### 4. PARTICIPANTS AND RECRUITMENT

#### 4.1. Recruitment

Participants will be recruited through an online recruitment panel (Prolific) in which participants are compensated proportionate to the time it takes to complete the online study ( $\approx$  £5/hour reward participants).

Participants' recruitment will be stratified by gender (50% male, 50% female), student status (3.5% yes and 96.5% no) [19] and qualification levels; the proportion of low (below level 4) versus high (level 4 or above) qualification levels will be based on current population statistics from the Labour Force Survey (LFS) 2013 for adults aged 19-64 in England [20]:

- **60% lower qualification levels**
  - No formal qualifications
  - 1–3 GCSEs or equivalent

*(Level 1: first certificate; GCSE - grades 3, 2, 1 or grades D, E, F, G; level 1 award; level 1 certificate; level 1 diploma; level 1 ESOL; level 1 essential skills; level 1 functional skills; level 1 national vocational qualification (NVQ); music grades 1, 2 and 3)*

- 4+ GCSEs or equivalent

*(Level 2: CSE - grade 1; GCSE - grades 9, 8, 7, 6, 5, 4 or grades A\*, A, B, C; intermediate apprenticeship; level 2 award; level 2 certificate; level 2 diploma; level 2 ESOL; level 2 essential skills; level 2 functional skills; level 2 national certificate; level 2 national diploma, level 2 NVQ; music grades 4 and 5; O level - grade A, B or C)*

- A level or equivalent

*(Level 3: A level; access to higher education diploma; advanced apprenticeship; applied general; AS level; international Baccalaureate diploma; level 3 award; level 3 certificate; level 3 diploma; level 3 ESOL; level 3 national certificate; level 3 national diploma; level 3 NVQ; music grades 6, 7 and 8; tech level)*

- **40% higher qualification levels**

- Certificate of higher education (CertHE) or equivalent

*(Level 4: certificate of higher education (CertHE); higher apprenticeship; higher national certificate (HNC); level 4 award; level 4 certificate; level 4 diploma; level 4 NVQ);*

- Diploma of higher education (DipHE) or equivalent

*(Level 5: diploma of higher education (DipHE); foundation degree; higher national diploma (HND); level 5 award; level 5 certificate; level 5 diploma; level 5 NVQ)*

- Bachelor or equivalent

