#### Independent variables

##### **SEP**

#### **Level of education**

- **Highest educational qualification** will be coded from 1 to 9: 1 = No formal qualifications; 2 = 1–3 GCSEs; 3 = 4+ GCSEs; 4 = A level; 5 = Certificate of higher education (CertHE); 6 = Diploma of higher education (DipHE); 7 = Bachelor; 8 = Master’s degree; 9 = Doctorate, and as a binary variable as *lower* (values: 1, 2, 3, 4) or *higher* (values: 5, 6, 7, 8, 9).
- **Years in higher education**, as a continuous variable
- **Level of education (composite score):** In order to account for years in higher education and highest education qualification when characterising each participants’ education level, we will z-score the two variables and create an average of the two to form a composite score called ‘*level of education*’.

**Equivalent household disposable income:** The OECD-modified equivalence scale will be used to adjust household income, taking into account household size and composition [24]. Equivalent income will be calculated by dividing the after tax household income by the sum of the equivalence value of all the household members: first adult = 1, additional adult or child aged 14 and over = 0.5, child aged 0-13 = 0.3.

**Subjective SEP:** The measure of the Subjective Social Status using the MacArthur Scale will be coded from 1 to 10.

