#### 7.6. Sensitivity analyses

Sensitivity analyses will be conducted to examine whether the pattern of results from the primary analyses differ after excluding participants guessing the aims of the study.

We will repeat our main analyses with a more stringent criteria for having completed the shopping task as intended (excluding any participants who did not select 10 items in total and 1 item from each category on the shopping list).

We will also repeat the main analysis substituting the composite variable *level of education* by *years in higher education* as a continuous covariate (ANCOVA) and by *highest educational qualification* split into lower vs. higher qualification levels as a binary covariate (2x2x2 ANOVA).

We will report whether sensitivity analyses result in deviations from the pattern of significance to the main analyses (i.e., any significant differences between conditions becoming not significant, and vice versa).

[figure not shown]

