#### **7.8. Sample size**

##### To observe differences between the intervention groups and interaction with SEP

In a previous study (n=1,088) using the online supermarket platform, two types of nutritional interventions targeting a reduction of saturated fat (SFA) were compared: 1/ altering the default order of products in ascending order of SFA content 2/ offering explicit swaps with lower SFA [28]. This study showed a large main effect (f=0.42) of altering the default order: -4.78% (95%IC: -5.43 to -4.12) of energy from SFA; and a small-to-medium main effect (f=0.12) of offering swaps: -1.48% (95%IC: -2.19 to -0.76) of energy from SFA. Regarding ED reduction, this study showed a small-to-medium main effect (f=0.14) of altering the default order: -5.16 (95%IC: -7.3 to -3.02); and no significant main effect (f=0.04) of offering swaps -1.5 (95% IC: -3.65 to 0.67).

Based on these previous results, we will power our analyses to detect small main effects (f=0.1) of the *labelling* and *increased proportion* interventions. In an ANCOVA including four groups (*control*, *labelling*, *increased proportion*, *increased proportion & labelling*) and one covariate (*level of education*), to detect a main effect of *labelling* or *increased proportion* we will require a sample size of 788 participants (197 per group) for 80% power at  $\alpha = 0.05$  (GPower 3.1).

A sample size of 788 participants will allow to detect small interaction effects (f=0.1) of *labelling* or *increased proportion* with *level of education* in an ANCOVA including four groups (*control*, *labelling*, *increased proportion*, *increased proportion & labelling*) and one covariate (*level of education*) for 80% power at  $\alpha = 0.05$  (GPower 3.1).

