**5. What is your highest educational qualification? If you are a student please select the diploma being studied for.**

- No formal qualifications
- 1–3 GCSEs or equivalent
- 4+ GCSEs or equivalent
- A level or equivalent
- Certificate of higher education (CertHE) or equivalent
- Diploma of higher education (DipHE) or equivalent
- Bachelor or equivalent
- Master’s degree or equivalent
- Doctorate or equivalent

**6. After leaving school (i.e. at 16 years old), how many further years of higher education (i.e. a formal course) did you study for?**

*Examples:*

*If you left school and did not go on to study further in higher education, your answer would be 0.*

*If you left school and then studied for two years for A levels, your answer would be 2.*

*If you completed A levels over two years and then also studied for a three year undergraduate degree, your answer would be 5.*

\_\_ (free text)

**7. What is your annual after tax household income, including all earners in your household, in GBP (to the nearest £1000)?**

£\_\_\_\_ (free text; range 0-999,999)

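### Section 7.6 does not say that years in higher education are centred; with raw years, the labelling and proportion tests would refer to people with no post-16 study

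*Combined protocol and SAP*

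**What the plan says.** Section 7.3 (Level of education) builds the primary socioeconomic covariate from highest qualification and years in higher education: "we will z-score the two variables and create an average of the two to form a composite score". Years on their own are defined only "as a continuous variable".

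Section 7.5 fits an ANCOVA with labelling, proportion, education and the two products labelling × education and proportion × education.

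Section 7.6 repeats this model with years replacing the composite, "as a continuous covariate (ANCOVA"), and again with qualification as a lower/higher binary variable. It then reports as a deviation "any significant differences between conditions becoming not significant, and vice versa".

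Appendix E item 6 fixes the zero of the years scale: "If you left school and did not go on to study further in higher education, your answer would be 0". Its next example reads "If you left school and then studied for two years for A levels, your answer would be 2", and A levels followed by a three-year degree count as 5.

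No section says that years are centred or standardised in the section 7.6 model, at what education value the condition terms are tested, or which type of sums of squares is used.

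**The concern.** When a model contains a labelling × education product, the labelling coefficient and its Type III test describe the labelling effect where education equals zero. For the composite, zero is average education, provided the z-scores are formed in the analysed sample. For raw years, zero is a person with no study after 16. The primary and sensitivity tests would then answer different questions, and the second would be less precise.

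The reporting rule in section 7.6 compares the two by significance alone. A labelling or proportion effect that is significant in the primary model but not in the years model would be reported as sensitive to the education measure, when the cause could be the move of reference point. The effectiveness of both interventions is part of the primary objective in section 2, and section 7.8 sizes the trial for their main effects, so such a report would cast doubt on a headline result.

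**Working it through.** **The plan's own figure.** Section 7.8 gives 788 participants for f = 0.1, 80% power and α = 0.05, with four groups and one covariate. A noncentral F with df1 = 1, df2 = N − 5 and λ = f²N gives N = 787, rounded to 788 for four equal groups; power at 788 is 0.801. The figure reproduces.

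**What the coefficient tests.** Write the model as Y = β0 + β1L + β2P + β3E + β4L·E + β5P·E. The labelling effect at E = e is β1 + β4e, so β1 is the effect at E = 0.

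**Its variance.** Let raw years have mean m and SD s. With equal arms and education independent of arm, the estimated effect at the mean has variance 4σ²/N. The interaction slope has variance 4σ²/(N·s²) and is uncorrelated with it. The effect at zero years is the effect at the mean minus m times the slope, so its variance is (4σ²/N)·(1 + m²/s²). The inflation factor is 1 + (m/s)².

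**Assumed years.** The documents give no mean or SD. I use the section 4.1 quota ("60% lower qualification levels", 40% higher) and the Appendix E example values. The lower group reports 2 years with probability a (the A-level share) and otherwise 0; the higher group reports 5. Then m = 2 + 1.2a and s² = 10 + 2.4a − m². A fourth case takes a = 0.5 and spreads the higher group over 3, 4, 5, 6 and 9 years with weights .10, .10, .50, .25 and .05. This gives m = 0.6×1 + 0.4×5.15 = 2.66 and s² = 0.6×2 + 0.4×28.05 − 2.66² = 5.34.

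**Power.** For a uniform effect the noncentrality is f·√788 / √(1 + (m/s)²). Without inflation it is 2.81 at f = 0.10, 3.93 at f = 0.14 and 5.61 at f = 0.20. The value 0.14 is the energy-density effect cited in section 7.8 ("small-to-medium main effect (f=0.14) of altering the default order"). A flip is p < 0.05 with the composite and p ≥ 0.05 with raw years. Flip rates come from simulated trials at N = 788 with no true interaction: 6,000 per scenario, except the spread case at f = 0.20, which used 3,000.

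| | a = 0 | a = 0.5 | a = 1 | a = 0.5, higher group spread |
|---|---|---|---|---|
| Mean, SD of years | 2.0, 2.45 | 2.6, 2.11 | 3.2, 1.47 | 2.66, 2.31 |
| Variance inflation | 1.67 | 2.52 | 5.74 | 2.32 |
| Power on raw years, f = 0.10 | 58.5% | 42.4% | 21.6% | 45% |
| Flips, f = 0.10 | 30% | 50% | 75% | 47% |
| Power on raw years, f = 0.14 | 86.1% | 69.7% | 37.5% | 73% |
| Flips, f = 0.14 | 13% | 29% | 62% | 25% |
| Power on raw years, f = 0.20 | 99.2% | 94.2% | 64.9% | 96% |
| Flips, f = 0.20 | 1% | 6% | 36% | about 4% |

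With the composite or z-scored years, simulated power is 79–81% at f = 0.10, 97–98% at f = 0.14 and 100% at f = 0.20. Replacing the composite by z-scored years flips 0.1% of significant results or fewer at f = 0.10.

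**A wider range.** For means of 2 to 4 years and SDs of 1.5 to 2.5, the inflation runs from 1 + (2/2.5)² = 1.64 to 1 + (4/1.5)² = 8.11, and power at f = 0.10 from 59% down to 17%.

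**If the hypothesised interaction exists.** Take mean 3, SD 2, a labelling effect of −0.2 SD at mean education, and the planned interaction (f = 0.1) in the expected direction. The effect at zero years is −0.2 + 0.2×(3/2) = +0.1 SD, which reverses the sign. In 2,000 simulated trials with years drawn around these values, rounded and floored at zero, the labelling test was significant in 81% with standardised years and 14% with raw years. With half that interaction the figures were 79% and 6%. The interaction test itself was the same on both scales (80% and 29%).

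**Binary model.** With qualification coded ±0.5 and a 60/40 split, the mean is −0.1 and the variance 0.24, so the inflation is 1 + 0.01/0.24 = 1.04. Power at f = 0.10 is 78–79%, and this model stays significant in about 97% of the raw-years flips.

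**The case against.** The plan is silent on centring; it does not state a wrong rule. The harm needs two things together: raw years in the model, and the coefficient or Type III test read as the condition effect. Years are z-scored while forming the composite, so an analyst might reuse that variable. A difference between conditions could also be read as an adjusted difference at mean education, which does not move, and Type II tests would not move either. This stands as a limit on the claim. But the plan z-scores years only as an ingredient of the composite and defines the stand-alone variable without it, so the literal reading is raw years.

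The directional socioeconomic hypotheses are interaction questions and do not depend on centring. If an interaction is found, section 7.5 turns to floodlight analysis, which is also unaffected. That protection is partial: at half the planned interaction, the interaction test is significant in only 29% of trials.

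The a = 1 column is an extreme. It needs every lower-group participant to report exactly 2 years and every higher-group participant exactly 5. Section 4.1 puts a wide span of qualifications in each group, so the spread column is the more plausible one.

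No decision hangs on the section 7.6 report, and the binary model would usually stay significant beside a lost result, which could alert a careful reader. The plan does not ask for that comparison. Finally, the opposite error, an effect gained at zero years, has not been quantified.

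**Conclusion.** The concern holds, and it is minor. That raw years move the condition tests to zero post-16 years, with variance multiplied by 1 + (mean/SD)², is algebra and needs no assumed data.

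The size of the loss does rest on assumed years. Under the more varied case, with a uniform effect, about half of significant primary condition effects at f = 0.10 and a quarter at f = 0.14 would be reported as deviations. At f = 0.20 the problem nearly disappears. Other distributions of years could fall outside the ranges shown.

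The problem is confined to the labelling and proportion terms in one sensitivity model. The primary analysis, both interaction tests, the Johnson–Neyman region, the sample size of 788 and any condition effect estimated at mean years are untouched, and the binary model is nearly so.

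**What to change.** Add one sentence to section 7.6: years in higher education enter the model as the z-score already computed for the composite, or mean-centred in the analysed sample. Equivalently, state that labelling and proportion effects are tested at mean years. It would help to name the type of sums of squares and to confirm that the z-scores are formed in the analysed sample.

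The cost is one sentence in the plan. The z-scored variable already exists, and nothing changes in data collection, sample size, primary analysis or interaction tests.

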## 7. STATISTICAL ANALYSIS

All statistical analyses will be performed using SAS version 9.3 (SAS Institute, Inc., 2012 SAS® 9.3. Cary, NC). The level of significance will be set at  $p < 0.05$  for primary and sensitivity analyses and at  $p < 0.01$  for secondary analyses.

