#### 7.5. Primary analyses

The measure of SEP used in our primary analysis will be the *level of education* because previous research showed that people of higher education were more likely to use nutrition labels [32], [33].

**ANCOVA** will be used to test the effect of *labelling* (categorical variable: yes or no), *proportion* (categorical variable: default or increased), *level of education* (continuous variable) and *labelling\*level of education* and *proportion\*level of education* interactions on the *mean ED of foods purchased*. If this analysis reveals the predicted significant interaction between *labelling* or *proportion* condition and the continuous measure of *level of education* on *mean ED*, we will further examine the nature of the interactions by conducting floodlight analysis [34]. We will calculate the Johnson–Neyman point defined as the value of *educational level* for which the effect of *labelling* (or *proportion*) reaches statistical significance [35]. Values of *level of education* above this point will correspond to significant differences between the *labelling* and *no labelling* conditions (resp. the *default* and increased *proportion* conditions) whereas values below the point will not. The floodlight analysis will be run using the SAS macro developed by Hayes & Matthes, 2009 [36].

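### Section 7.6 checks qualification only as a lower/higher split, so a real education interaction may seem not to replicate simply because that check is weaker

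*Combined protocol and SAP*

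**What the plan says.** Section 7.3 (Level of education) states that highest qualification "will be coded from 1 to 9: 1 = No formal qualifications", rising to 9 for a doctorate. It also defines a binary version, codes 1-4 against 5-9. The primary measure is a composite: the mean of the z-scored 1-9 code and z-scored years in higher education.

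Section 7.5 enters this composite as a continuous covariate in an ANCOVA with labelling, proportion and the two intervention-by-education interactions.

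Section 7.6 then replaces the composite in two ways. Years stay continuous. Qualification is "split into lower vs. higher qualification levels as a binary covariate (2x2x2 ANOVA"). Results are compared by whether significant findings lose significance or the reverse. Section 7 sets p < 0.05 "for primary and sensitivity analyses and at" p < 0.01 for secondary analyses.

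On power, Section 7.8 states: "A sample size of 788 participants will allow to detect small interaction effects (f=0.1"), at 80% power. It gives no power for any sensitivity analysis.

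**The concern.** The two components of the composite are treated differently, and no reason is given. Years keep their full range. Qualification loses its own, so that no qualifications counts the same as A level, and CertHE the same as a doctorate.

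This matters because of how the check is read. The leading hypothesis is that labelling works better at higher SEP, which is an education interaction, and interactions with education are where coarsening education costs most. When the criterion is a change in significance, a check with less power produces apparent non-robustness even if the interaction is real and does not depend on the measure. It also works the other way: the plan predicts equal effects of proportion across SEP, and a weaker interaction test gives a non-significant result more readily.

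**Working it through.** **Inputs from the plan.** Alpha 0.05 (Section 7); f = 0.1, N = 788, 80% power (Section 7.8); cut between codes 4 and 5 (Section 7.3); recruitment 60% lower and 40% higher (Section 4.1).

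**Assumptions, not in the plan.** Moderation linear in the composite; the distribution of education; a qualification-years correlation ρ of 0.7 to 1.

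**1. The plan's own figure.** λ = N·f² = 788 × 0.01 = 7.88. A noncentral F test with 1 and 783 df gives 80.06% power, and the smallest N reaching 80% is 787. The stated 788 reproduces.

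**2. Additional ANOVA terms.** A full 2x2x2 factorial has 780 residual df. With λ still 7.88, power is 80.06%, so the extra terms cost nothing.

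**3. The split, normal education.** If r is the correlation between the binary measure and the continuous moderator, λ is multiplied by r². For a normal variable cut 60/40, r = φ(0.253)/√(0.6 × 0.4) = 0.789 and r² = 0.622. Then λ = 7.88 × 0.622 = 4.90 and power is 59.9%. If all 1,000 recruited were analysed, λ = 10 × 0.622 = 6.22 and power is 70%.

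**4. The split, discrete codes.** The composite correlates √((1+ρ)/2) with the 1-9 code, so r = r(code, split) × √((1+ρ)/2). The percentages for codes 1 to 9 below are assumed; each puts 60% in codes 1-4.

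| Assumed % in codes 1-9 | r(code, split) | Power, ρ=1 | ρ=0.8 | ρ=0.7 |
|---|---|---|---|---|
| 5,10,20,25,6,6,18,8,2 | 0.880 | 69.4% | 64.8% | 62.3% |
| 1,4,20,35,3,5,22,8,2 | 0.911 | 72.3% | 67.8% | 65.3% |
| 12,15,18,15,8,8,12,8,4 | 0.874 | 68.8% | 64.2% | 61.8% |
| 1,4,15,40,15,10,10,4,1 | 0.820 | 63.3% | 58.8% | 56.4% |

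The range is about 56% to 72%.

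**5. The uncut code.** Here r² = (1+ρ)/2, which is 0.85, 0.90 and 0.95 for ρ = 0.7, 0.8 and 0.9. Then λ = 6.70, 7.09 and 7.49, and power is about 73%, 76% and 78%. Dropping years therefore accounts for the smaller part of the loss and the split for the larger.

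**6. Main effects.** If the two education groups are weighted equally, λ is multiplied by 4 × 0.6 × 0.4 = 0.96, giving 7.56 and 78.4% power. Otherwise power stays at 80.1%.

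**7. How often the verdicts differ.** Trials were simulated at N = 788 with a true labelling-by-education effect of f = 0.1, fitting both planned models.

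- Normal education: power 79.8% (primary) and 59.3% (split). The two disagreed in 25% of trials, and 29% of significant primary interactions lost significance.
- First distribution in the table, ρ = 0.75: 79.5% and 63.6%; 21% disagreed and 23% were lost.
- Uncut code in the primary model, ρ from 0.7 to 0.9: 12% down to 6% were lost.
- Labelling main effect: at most 0.1% of trials lost significance. Where its verdict changed (9-10% of trials), it was almost always a gain, because equal weighting of the groups averages the effect at a different point on the education scale.

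**The case against.** There is a real case for the split. It is pre-specified, it follows the recruitment strata of Section 4.1, and it matches hypotheses worded in terms of higher and lower SEP. It is also the only education check that assumes neither linearity nor equal spacing of levels. If moderation were a step at level 4, the binary model would not be the weaker one. The uncut code correlates 0.92-0.97 with the composite at ρ = 0.7-0.9, so it comes close to re-running the primary analysis. Years, kept continuous, already provides a check that changes only the measure. All of this stands, and it is why the split should be kept. It does not make a change of significance under the split readable as dependence on the education measure.

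A reader might infer that the 2x2x2 ANOVA itself causes the power loss. Step 2 shows that it does not. It is not even certain that a full factorial is meant, since Section 7.6 presents this as the main analysis with one variable replaced. If it is meant, labelling-by-proportion and a three-way term enter a model that otherwise omits them. That blurs interpretation, but power is unaffected.

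A reader might also infer that the whole check runs at 60% power. Only the education interactions are affected.

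**Conclusion.** The point holds for the intervention-by-education interactions. With linear moderation at f = 0.1 and N = 788, power falls from 80% to about 60% under normal education, and to roughly 56-72% over the assumed distributions and correlations. Given a real interaction and a significant primary result, about 23-29% of checks would lose significance with the split, against 6-12% with the uncut code. The difference between those two bands is what the split adds; the rest comes from dropping years.

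The 60% is not a figure in the plan. It depends on a distribution of education that the documents do not give, on linearity and on the minimum sample, and the loss rates move with the same assumptions. Nor do the documents support reading this as a flaw in the primary analysis, which uses the continuous composite, or as grounds for dropping the binary analysis. What is weakened is the robustness statement about the central SEP hypothesis.

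**What to change.** In Section 7.6:

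1. Add an analysis with highest educational qualification (1-9 code, z-scored) as a continuous covariate in the same model as the primary analysis: labelling, proportion, education and the two intervention-by-education interactions.
2. Keep the lower/higher analysis as a supplementary check of functional form, and state that it uses the primary model's terms.
3. Report the interaction estimates with 95% confidence intervals side by side for all education measures, instead of only whether significance changes. Continuous measures should be on a common (z-scored) scale, and the lower/higher contrast should be labelled as such because its coefficient is in different units.

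The cost is one more model on data already collected. The uncut code assumes equal spacing of the nine levels, which the composite already does.
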